6.5.5.1 Reactions to In-Clinic Dosing (Group 1)

6.5.5.1.1 Up-dosing Tolerated at First Dose at New Dose Level

The scenarios listed below describe a subject considered to have tolerated the first dose at a new dose level. The procedures outlined for each scenario should be followed.

- No symptoms: If a subject undergoes up-dosing in the CRC without symptoms, the action should be to continue, per protocol, with daily home dosing at the tolerated dose level and return to the CRC for the next scheduled dose escalation visit 2 weeks later.
- Oral/pharyngeal pruritus only: If the subject experiences *oral/pharyngeal pruritus* only following the administration of the first dose at a new dose level, the dose will generally be *assessed as tolerated*, and the same dose can be repeated the next day at home and continued throughout the 2-week home-dosing interval, unless other symptoms indicative of lack of tolerability begin to develop.
- Mild symptoms, tolerated at first dose at new dose level (see [Section 6.5.1](#) for definitions of mild symptoms): If *mild symptoms* occur with the first dose at a new dose level and the dose is *assessed as tolerated*, the action taken should be to repeat the same dose the next day. It is advised that the repeat (next day's) dose be administered in the CRC, but it may be given at home, at the investigating physician's discretion. If the second dose at the new (increased) dose level is tolerated without symptoms, then the subject is to continue that dose level for the requisite 2 weeks and return to the CRC for up-dosing at the next scheduled visit. If the dose again causes mild symptoms, but is *assessed as tolerated*, the subject may continue at that dose level or return to the last tolerated dose (at the investigator's discretion) and continue dosing at home for the next 2 weeks at the investigator-determined dose level. (See [Section 6.5.5.2](#) for actions to be taken in the event that symptoms develop during home-dosing.) If, following the first dose at a new dose level, the second dose at the new (increased) dose level is again accompanied by mild symptoms, but is *assessed as not tolerated*, the procedures outlined in the paragraph above should be followed. The algorithm for management of dose adjustments due to poorly tolerated doses is depicted in [Figure 3](#). Explanatory text follows the figure.

Figure 3: Schematic for Management of Dose Adjustments due to Poorly Tolerated Doses (Groups 1 and 2)

- Mild symptoms that indicate uncertainty regarding tolerability: If *mild symptoms* (see [Section 6.5.1](#) for definitions of *mild symptoms*), other than *oral/pharyngeal pruritus* occur with the first dose at a new dose level and there is uncertainty about whether the dose is tolerated, the investigator will determine whether the subject should receive the next dose in the CRC or at home. If the investigator determines that the subject requires medical supervision to determine tolerability, the subject should receive the next dose at the CRC. If the investigator determines that the subject does not need medical supervision, the procedure will be to split the home dose into 2 doses taken 8 to 12 hours apart.
- Mild symptoms that indicate lack of tolerability: If *mild symptoms* other than *oral/pharyngeal pruritus* occur with the first dose at a new dose level and the dose is *assessed as not tolerated*, the action taken should be to have the subject return to the CRC the next day for dosing at the last tolerated dose (ie, a 1-step dose reduction) under medical supervision (if the subject is unable to return to the CRC on the day specified, the investigator may initiate an approximate 1 dose-level reduction at home, with the subject coming to the CRC at the earliest date possible).

If the reduced dose is *assessed as tolerated*, the subject is to continue that daily home dose for the ensuing 2 weeks. (See [Section 6.5.5.2](#) for actions to be taken in the event that symptoms develop during home-dosing.) If the reduced dose is again *assessed as not tolerated*, the subject is to return to the CRC the next day for supervised dosing at a 1- or 2-step reduction in dose (per investigator judgment, based on severity of reaction). If this further reduced dose is *assessed as tolerated*, the subject will continue at that dose level for daily home-dosing over the ensuing 2 weeks. If, however, the reduced dose is *assessed as not tolerated*, the subject is to be considered an escalation failure non-responder.

- Moderate symptoms occurring with a new dose level would indicate lack of tolerability, with rare exceptions. Exceptions would generally be for a transient, self-limited (requiring no intervention and resolving completely) symptom of moderate intensity occurring in a single organ system. In addition, the symptom would typically be subjective. Any dose associated with moderate symptoms and assessed as tolerated must be accompanied by a brief explanation in the CRF as to why the dose was considered tolerated; (see [Section 6.5.2](#), for moderate symptoms assessed as tolerated). If moderate symptoms occur with the first dose at a new dose level, except for rare instances described above, the dose will be *assessed as not tolerated*. The action taken should be to have the subject return to the CRC the next day for dosing at the last tolerated dose under medical supervision. If this reduced dose elicits no allergic symptoms (ie, is well tolerated), the subject will continue that daily home dose level for an additional 2 weeks.

If the subject experiences mild symptoms at the reduced dose, the procedures for responding to a dose with mild symptoms should be followed (see above). If the subject experiences moderate symptoms at the reduced dose level, the subject should return to the CRC the next day and receive a further 1- or 2-step dose reduction (per investigator judgment). If this reduced dose is well tolerated, it will be continued as the daily home dose for ≥ 2 weeks before re-escalation is attempted in the CRC. If the dose is not well tolerated, but elicits mild symptoms, then the treatment procedures for responding to mild symptoms should be followed (see above). If, however, the subject again experiences moderate symptoms at the reduced dose level, a discussion with the Medical Monitor is to ensue to reach a decision as to whether to continue the subject in the study.

In the rare instance that a dose eliciting moderate symptoms is *assessed as tolerated*, then the actions taken should be the same as for a dose with mild symptoms *assessed as tolerated*.

- Severe symptoms (these always indicate lack of tolerability): If *severe symptoms* occur, the action should be to treat the subject for the allergic reaction, and then, in consultation with the Medical Monitor, decide whether or not to discontinue the subject from the study. If it is determined that it is safe to allow the subject to continue in the study, the subject should return to the CRC the next day for dosing at a 2-step reduction in dose under observation. If the subject tolerates the dose reduction (ie, shows no or only mild symptoms that are assessed as tolerated), then the subject is to remain at the reduced dose level for ≥ 2 weeks before returning to the CRC to attempt dose re-escalation. If the subject does not tolerate the reduced dose, then the subject is to be considered an escalation failure non-responder.

Severe symptoms requiring 0 to 1 dose of epinephrine: If a subject experiences severe symptoms requiring 0 to 1 dose of epinephrine, the procedure is to have the subject return to the CRC for the next dose and to reduce the dose by 2 dose levels. If no or mild symptoms (assessed as tolerable) occur, dosing may proceed at the reduced level for at least 2 and up to 4 weeks. If moderate or severe symptoms occur, dosing is to be discontinued.

Severe symptoms requiring 2 doses of epinephrine: If a subject experiences severe symptoms requiring 2 doses of epinephrine, the procedures outlined in the above paragraph should be followed; however, dosing will proceed at the reduced dose level (if tolerated) for at least 6 and up to 8 weeks.

For specific questions related to dose-escalation or continuation of the same dose that are not answered in the above protocol, the Medical Monitor will be available for consultation.

6.5.5.1.2 Up-dosing: Tolerability Uncertain or No Tolerability at First Dose at New Dose Level

If a subject has symptoms in the CRC after up-dosing that suggest the dose was not tolerated, or suggest that tolerability of the dose is uncertain, the investigator must assess the tolerability, as outlined in [Section 6.5.3](#). The algorithm for management of dose adjustments due to poorly tolerated doses is depicted in [Figure 3](#). Explanatory text follows the figure.

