Based on experience from Phase 2, most acute allergic responses to dosing that are characterized by mild symptoms would be anticipated to meet the above criteria. If, however, an allergic response to dosing is characterized by mild symptoms that do not meet all of the above criteria (eg, has mild symptoms occurring in 2 or more organ systems, requires treatment with 2 doses of antihistamine or 1 dose epinephrine, shows progression in severity or distribution over time, is protracted in duration, or includes objective wheezing), then even though the allergic symptoms may be mild, the dose should be assessed to be not tolerated. If a dose elicits mild symptoms that do not fit all of the above criteria and the dose is assessed to be tolerated, then a brief explanation as to why the dose was considered tolerated must be recorded in the CRF.

Moderate symptoms: In general, if a dose elicits moderate symptoms, the dose will be assessed as not tolerated. There may, however, be rare occasions when a dose eliciting moderate symptoms could be assessed as tolerated. Generally, this would only be the case for a transient, self-limited (requiring no intervention and resolving completely) symptom occurring in a single organ system. In addition, typically the symptom would be subjective only. Any dose associated with moderate symptoms and assessed as tolerated must be accompanied by a brief explanation in the CRF as to why the dose was considered tolerated.

Severe symptoms: If a dose elicits severe symptoms, the dose will be assessed as not tolerated. Whenever a dose elicits an allergic response characterized by 1 or more severe symptoms, the crucial decision, after adequate treatment for the allergic reaction has been administered, will be to determine whether the subject should continue in the study, dosing at a reduced dose level, or be discontinued early from the study. Please refer to individual stopping rules in [Section 7.8.2](#).

The determination of tolerability will decide the course of action to be taken in response to dose-related reactions ([Section 6.5.3](#)).

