6.5.5 Treatment for Reactions During the Up-dosing Period (Group 1): Dose Adjustment

If a dose or dose level is assessed *as not tolerated*, the action taken will depend on the type and severity of the dose-related reaction and the investigator's clinical judgment. The following possible actions are at the investigator's discretion and are considered in greater detail in subsequent sections ([Section 6.5.5.1](#), [Section 6.5.5.2](#), [Section 6.5.5.3](#), and [Figure 2](#)).

- Dosing the subject under medical supervision in the CRC – this is encouraged whenever there is question as to the tolerability of a dose level. It may be performed at the current dose level or at a reduced dose level, if there is already a high index of suspicion that the current dose level has not been tolerated.
- Holding dose level at current level for an additional 1 to 2 weeks before attempting dose escalation – this may be done at the discretion of the investigator if there is concern that the current dose level has not been sufficiently well tolerated to attempt up-doing to the next dose level.
- Reducing dose by 1 or 2 dose levels and maintaining the reduced dose level for 2- to 4-week period before attempting dose re-escalation – Generally, this should be the action taken when a dose that has been observed in the CRC is assessed as not tolerated, if a dose elicits moderately severe symptoms, if a single dose of epinephrine has been administered to treat a dosing reaction, or if the investigator is convinced of the intolerability of the current dose level. In short, it should be considered the default action whenever a dose or dose level is assessed *as not tolerated*.
- Reducing dose level for less than the usual 2-week period – this may be instituted as treatment for an intercurrent AE, to aid the investigator in determining if a dose level is or is not tolerated, or if a pattern of decreased study product tolerability during menses is discerned. The level of the reduction in dose, ranging from a 1-step reduction to a 50% reduction will be at the investigator's discretion, based on clinical judgment. The manner in which dose escalation may resume will depend on the level and the duration of the dose reduction.

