Epinephrine: single dose given in CRC	
 Stop dosing at CRC Reduce next dose by 2 doses, both to be administered at CRC Continue bi-weekly escalation
Epinephrine required for a second consecutive time during, or after, 1 escalation attempt	
 Dose reduced by 2 dose levels. Reduced dose level continued for 6 to 8 weeks Escalation may be attempted after 6 to 8 weeks
Epinephrine required for a third consecutive time during an escalation attempt	
 Discontinue dosing Subject returns to CRC 14 days after last dose for Early Discontinuation Visit
Epinephrine: single dose at home	
 Not counted in the total count of epinephrine uses unless severe anaphylaxis has occurred Subject returns to CRC for an observed dose under medical supervision prior to resuming any dosing at home

CRC = clinical research center.

- Antihistamines
If a subject receives antihistamines only, the dose escalation can be continued. If epinephrine is administered, then a different course of action is to be taken (see below).
- Epinephrine – General Procedures
Any reaction to study product (in clinic or at home) that requires more than 2 doses of epinephrine will halt all further dosing of study product for the individual. The subject will be asked to return to the CRC 14 days following the last dose of study product to undergo an Early Discontinuation Visit ([Section 6.3.10](#)).
- Epinephrine – Single Dose Administered at Clinic
If a single administration of epinephrine is required during or after a dose-escalation in the clinic, no further dosing of study product is to occur at that visit. The next dose of study product is to be reduced by 2 dose levels and administered in the CRC, but biweekly dose escalation should continue.
If a single administration of epinephrine is required for a second consecutive time during, or after, 1 escalation attempt, the dose should be reduced by 2 dose levels, and the subject continued at that dose level for 6 to 8 weeks. After 6 to 8 weeks at the reduced dose, an escalation attempt may be tried in clinic.

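### Table 7 ends dosing after two epinephrine doses for one up-dosing reaction where the rest of the protocol continues it; the step-down after one in-clinic dose is also not stated consistently

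*Protocol*

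**What the plan says.** **Two doses for one reaction.** Table 7 (Protocol 6.5.6, as read from the PDF) stops dosing once two or more epinephrine doses have been given, in clinic or at home, and calls for an Early Discontinuation Visit 14 days after the last dose. Four other places differ:

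- 6.5.5, dose adjustment list: after two doses for a single AE, a 2-level reduction held for at least 6 weeks before re-escalation is mandatory.
- 6.5.5.1.1, severe symptoms with two doses: dosing continues 2 levels lower, if tolerated, for 6 to 8 weeks.
- 6.5.6, general epinephrine text under Table 7: dosing is halted only when a reaction needs more than two doses.
- 7.8.2: three or more doses for a dose-related reaction is an individual stopping rule.

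**One dose given in clinic.** In 6.5.5.1.1, the path for mild symptoms judged not tolerated gives this instruction: "return to the CRC the next day for dosing at the last tolerated dose (ie, a 1-step dose reduction) under medical supervision". When coming in on that day is not possible, "the investigator may initiate an approximate 1 dose-level reduction at home". For moderate symptoms, "The action taken should be to have the subject return to the CRC the next day for dosing at the last tolerated dose". The default action in 6.5.5 is "Reducing dose by 1 or 2 dose levels and maintaining the reduced dose level for 2- to 4-week period before attempting dose re-escalation", and one of its triggers is "if a single dose of epinephrine has been administered to treat a dosing reaction". The single-dose rule in 6.5.6 is: "The next dose of study product is to be reduced by 2 dose levels and administered in the CRC". The matching Table 7 cell reads "Reduce next dose by 2 doses, both to be administered at CRC". Neither states a severity condition.

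The severity paths and the epinephrine rule can apply to the same subject. Section 6.5.2 treats a mild reaction as not tolerated if it "requires treatment with 2 doses of antihistamine or 1 dose epinephrine", and Table 6 lists epinephrine among the treatments for moderate symptoms.

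**The concern.** At exactly two doses, the table and the text give opposite instructions: one ends treatment, the other requires it to go on at a reduced dose. A site is likely to consult a table when managing a reaction. The choice feeds the secondary endpoint on AEs leading to withdrawal of AR101 (Protocol 9.2.2). The reach may extend past Group 1 up-dosing, because 6.5.7 applies the up-dosing procedures to QD Maintenance and QD Extended Maintenance.

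After one in-clinic dose, a site working from the severity paths goes down one level and a site working from 6.5.6 goes down two. The next dose after a reaction that needed epinephrine would then depend on which section was open.

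**Working it through.** **Two doses, set side by side**

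| Place | 2 doses, one reaction | 3 doses, one reaction |
|---|---|---|
| Table 7 | stop | stop |
| 6.5.5 | continue, 2 levels down, at least 6 weeks | not addressed |
| 6.5.5.1.1, severe | continue, 2 levels down, 6 to 8 weeks if tolerated | not addressed |
| 6.5.6 text | not halted | halt |
| 7.8.2 | not stopped | stop |

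More than two doses is the same as three or more, so the 6.5.6 text and 7.8.2 agree, and only the count of exactly two is in dispute. The Table 7 row cannot be read as cumulative use: the column is headed by the treatment given for the reaction, and repeated use on consecutive occasions has its own rows. Severe symptoms meeting stage 3 anaphylaxis stop dosing under 6.5.6 in any case, so the dispute is confined to two-dose reactions short of that.

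Continuing is feasible in the schedule. Assume re-escalation moves one Table 2 level per 2 weeks. Time until the reacting dose is retried = hold at 2 levels down + 2 weeks at 1 level down:

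- 6.5.5: at least 6 + 2 = at least 8 weeks, with no upper limit stated.
- 6.5.5.1.1, severe: 6 + 2 = 8 to 8 + 2 = 10 weeks.
- Slack in up-dosing: 40 − 22 = 18 weeks.

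**One dose, on the Table 2 ladder**

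Levels: 3, 6, 12, 20, 40, 80, 120, 160, 200, 240, 300 mg. The percent increases, 100 × (dose ÷ previous dose − 1), come out as 100, 100, 67, 100, 100, 50, 33, 25, 20, 25. All ten match Table 2.

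Ratio of the two possible next doses = (1 level down) ÷ (2 levels down):

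| Reacting dose (mg) | 1 level down | 2 levels down | Ratio |
|---|---|---|---|
| 12 | 6 | 3 | 2.00 |
| 20 | 12 | 6 | 2.00 |
| 40 | 20 | 12 | 1.67 |
| 80 | 40 | 20 | 2.00 |
| 120 | 80 | 40 | 2.00 |
| 160 | 120 | 80 | 1.50 |
| 200 | 160 | 120 | 1.33 |
| 240 | 200 | 160 | 1.25 |
| 300 | 240 | 200 | 1.20 |

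The range is 1.2 to 2.0. It reflects only the spacing of the ladder and is not weighted by where reactions occur. At a reacting dose of 6 mg, Table 2 has only one lower level (3 mg), so the two-level instruction cannot be followed.

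Time until the reacting dose is retried, in 2-week steps: 2 weeks from one level down, 2 + 2 = 4 weeks from two. The difference is 2 weeks.

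**The case against.** **On two doses.** Four places agree that dosing ends only above two, so the Table 7 cell may be a single slip. The symbols are not fully reliable in this text: the same ARC008 entry condition carries a strict inequality at 443 mg in the synopsis and a non-strict one in Section 3. A typing error or a PDF misreading cannot be excluded. This stands as a reason to check the original cell first. If the cell does read two or more, the contradiction is real whatever its origin.

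**On one dose.** The severity paths set a default and do not mention epinephrine, and 6.5.6 says a different course applies once epinephrine is given. The narrower rule normally prevails, and two levels down also satisfies the one-or-two range in 6.5.5. That range could also cover home epinephrine, which 6.5.6 treats separately. Much of this stands. A reader might infer that the sections cannot be reconciled, or that subjects face an unsafe dose. The documents do not support either: the higher dose is one the subject tolerated before, it is supervised by default, and only the mild path allows it at home, when the subject cannot return that day.

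What remains is that nothing says 6.5.6 overrides 6.5.5.1.1. The contrast in 6.5.6 is with antihistamines alone. Section 6.5.5 lists where its details are found and omits 6.5.6. Section 6.3.3.1 sends sites to 6.5.5 to set the lower dose by severity, and cites 6.5.6 only for delaying re-escalation. The severe path is split by epinephrine count, while the mild and moderate paths are not.

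**On what is not visible.** Figure 3, the algorithm for poorly tolerated doses, is not shown in the text reviewed and may branch on epinephrine. The one-dose point therefore concerns the prose and tables only. Whatever the figure shows, the Table 7 threshold would still disagree with the text beneath it.

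**Conclusion.** The two-dose rule is wrong as written, subject to checking the original Table 7 cell: at exactly two doses Table 7 discontinues a subject whom 6.5.5 requires to continue and whom neither the 6.5.6 text nor 7.8.2 would stop. The one-dose mismatch is secondary. Section 6.5.6 is the likely intent, but the text does not say so, and the two readings give next doses 1.2 to 2.0 times apart.

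The documents do not say how often either case occurs. A reader might divide one subject by the planned Group 1 size of 130 and report a shift of about 0.8 percentage points in the withdrawal frequency. That is not the reported denominator: planned sizes may vary (Protocol 7.8.3), and safety is generally summarised for ages 4 to 17 (SAP 6.3 and 10). A reader might also infer from the 18 weeks of slack that several two-level reductions always fit. They need not: 6.5.6 imposes 6 to 8 weeks after a second consecutive in-clinic use and ends dosing after a third.

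The analysis is descriptive (SAP 6.4), so no test or power figure changes. This is a matter of subject management and consistent conduct across sites.

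**What to change.** **Two doses.** Check the Table 7 cell in the original protocol. Change that row to more than two doses for one reaction, and add a row for two doses: 2 dose levels lower for at least 6 weeks. If discontinuation at two doses is what the sponsor wants, change 6.5.5, the severe path of 6.5.5.1.1, the general epinephrine text of 6.5.6, and 7.8.2 instead.

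**One in-clinic dose.** Add to 6.5.5 and to the mild-not-tolerated and moderate paths of 6.5.5.1.1 that, after a single in-clinic epinephrine dose, Section 6.5.6 governs: next dose 2 levels lower, in the CRC. Specify 3 mg for a reaction at 6 mg. Check that Figure 3 agrees.

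**Cost.** Protocol wording only, with no new procedure. The one-dose clarification adds about 2 up-dosing weeks for each affected subject compared with a one-level reduction.
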